## STUDY SYNOPSIS

Title of clinical Study («Study»)	Efficacy and safety evaluation of MONOBLUE DUAL View and MONOBLUE ILM View vital stains during vitrectomy surgery
Protocol Short Title Acronym	NewBlueDyes
Sponsor name	University Hospitals Leuven (UZ Leuven)>
Principal Investigator	[name]. [name]
Contact Address PI	UZ Leuven, [name]
Contact Email PI	[contact]
Contact Phone PI	[name]
Other public database nbr	NA
Coordinating Investigator	NA
Medical devices	Monoblue Dual View Monoblue ILM View
Study rationale	Retrospective Data Collection
Primary objective	Efficacy: visualization of membranes stained based on binary subjective evaluation.
Secondary objective(s)	

• Efficacy: subjective assessment of surgical help provided by the product

• Safety:

○ Rate and severity of potential study-related products adverse events

○ Visual outcome at the last postoperative visit

Endpoints	Effectiveness Outcomes: Improvement in BCVA after 2 months as compared to preoperative BVCVA. Safety Outcomes: Safety will be assessed based on incidence and severity of investigational device-related adverse events.
Time frame of collecting data for retrospective analysis	SEPTEMBER 2021-APRIL 2022

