### 2.3 Secondary Endpoints

- Efficacy: subjective assessment of surgical help provided by the product
- Safety:
  - Rate and severity of potential study-related products adverse events
  - Visual outcome at the last postoperative visit

The study hypothesis to be verified is non-inferiority in term of efficacy between study products and comparator based on a binary subjective evaluation of visualization of membranes stained. The proportion of success between study products and comparator will be studied, covariates (age, gender, visual acuity in the affected eye, surgery type being vitrectomy or phaco plus vitrectomy) taken into using a propensity score methodology.

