## 4 Statistics and Data Analysis

The primary outcome of the study is the success of the products based on assessment of efficacy of the staining dye.

Safety of the dye will be assessed by comparing the surgical outcome of the patients to a similar control group that underwent surgery using the staining dyes presently used in our department (see study endpoints).

Statistical analyses will be performed with R version 3.6.2 or higher. In case of missing values, the underlying missingness process (MCAR, MAR or MNAR) will be investigated and 15 multiple imputations will be performed using the **MICE** R package.

We will test with the statistical test of Jamshidian and Jalal (2010), implemented in the **MissMech** R Package (Jamshidian, Jalal & Jansen, 2014), whether missing data were MCAR. If they were not MCAR, we investigated whether or not the missing mechanism could be explained by baseline characteristics (eg, sociodemographic, medical features) of patients using logistic regression, which would suggest an MAR mechanism. If missing data were not MCAR or MAR, they were considered as MNAR.

For each dataset created, two propensity scores will be performed: a first one between the Monoblue ILM View and the ILM Blue, and a second one between the Monoblue Dual View and Membrane Blue Dual. The next covariates were selected for the propensity score: age, gender, visual acuity of the affected eye, surgery type of the affected eye (vitrectomy only vs phaco and vitrectomy). The Covariate Balancing Propensity Score provided in the R **CBPS** package (Imai & Ratkovic, 2014) will be used to estimate an Average Treatment Effect (ATE). The ATE will be estimated by covariate balancing and requesting an exact match. An absolute standardized difference less than 10–15% will be considered to support the assumption of balance between the groups. Unlike the P-value, this method is not affected by the sample size, and it could be used to compare the relative balance of variables that were measured in different units (Austin, 2011). Results (obtained after matching) will be expressed as the mean and standard deviation (SD) for continuous variables or the percentage for categorical variables. The **survey** R package will be used to perform linear regressions for continuous outcome variables and logistic regressions for binary variable. These regressions

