will include the treatment group effect, the weight resulting from the matching, and variables present in the propensity score. This procedure will provide a doubly-robust estimator, which corrected the last remaining possible imbalance between the covariates and produced an unbiased treatment effect (Funk et al., 2010). We will then combine results of the 15 regressions by taking the mean of the estimates of the regression coefficients of the treatment effect and the its associated p-value for each imputed dataset (the so-called, 'Mite approach'), as described by Leyrat et al. (2019). Adjusted P-values less than 0.05 will be considered significant.

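### For the continuous visual outcome, the default standard error of the weighted survey regressions is too small if a dye group is small and the weights are uneven

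*Combined protocol and SAP*

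**What the plan says.** Section 4 sets up one weighting exercise per dye pair ("two propensity scores will be performed: a first one between the Monoblue ILM View and the ILM Blue", and a second for the dual dyes). Four covariates enter: "The next covariates were selected for the propensity score: age, gender, visual acuity of the affected eye, surgery type of the affected eye". On the weights it says: "The ATE will be estimated by covariate balancing and requesting an exact match".

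For the outcome models, the survey "R package will be used to perform linear regressions for continuous outcome variables and logistic regressions for binary variable". These models "will include the treatment group effect, the weight resulting from the matching, and variables present in the propensity score". I read the weight as the regression weight, not as an extra covariate.

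The only error-rate figure is the threshold: "Adjusted P-values less than 0.05 will be considered significant". Sidedness is not stated. No variance estimator, small-sample correction, jackknife or bootstrap is named, and no sample size is given, only a collection window ("SEPTEMBER 2021-APRIL 2022" in the synopsis).

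Visual outcome at the last postoperative visit is a secondary endpoint in sections 2.3 and 5.2, and BCVA improvement appears in the synopsis. Its scale is not stated. I take it to be analysed by the linear regression that section 4 provides for continuous outcomes.

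**The concern.** With no variance method named, the package default applies: a linearised (sandwich) variance built from squared weighted residuals. A regression pulls its fit towards high-leverage points, so their residuals are smaller than the true errors. With few patients and uneven weights a handful of patients carry much of the leverage, and the sandwich variance comes out too small. The default makes no effective correction for this.

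The visual comparison with the control dyes is part of how section 4 judges safety, and section 2.1 says the results may lead the hospital to replace its standard dyes. A standard error that is too small produces chance visual differences called significant, and intervals that overstate what the data show.

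**Working it through.** **Inputs.** From the documents: threshold 0.05 (two-sided assumed), four covariates, ATE weights with exact balance, covariates repeated in the outcome model. Assumed: group sizes, degree of imbalance, complete data. There is no plan figure to reproduce, so the check is a simulation with no true dye effect.

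**Formulas.** Weights: w = T/e + (1-T)/(1-e), with e chosen so that the weighted covariate means agree exactly. With A = X'WX and weighted residual r:
- default variance: n/(n-1) × A⁻¹ (Σ w² r² xx') A⁻¹
- HC3: the same form with r replaced by r/(1-h), where h = w x'A⁻¹x is the leverage.

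The model has 6 coefficients (intercept, dye, four covariates), so leverages sum to 6. The average is 6/50 = 0.12 at 25 per group and 6/300 = 0.02 at 150 per group. Uneven weights push single values well above the average.

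**Continuous outcome, default standard error.** Two covariates shifted by 0.3 SD (modest) or 0.8 SD (strong), 1,500-3,000 data sets per cell:

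| Per group | Modest | Strong |
|---|---|---|
| 25 | 8.4% | 17.8% |
| 40 | about 7% | 12-13% |
| 80 | 5.8% | 9-10% |
| 150 | 5.2% | 7.4% |

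A separate run of this design gave 8.3% and 16.7% at 25/25, 9.1% and 16.7% at 25/100, and about 6-7% by 80-150 per group. A large control group therefore does not help if the study-dye group is small.

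A second design set imbalance by the SD of the propensity linear predictor (about 1,600-2,000 data sets, error about 0.5-1 point):

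| Groups | SD 0.5 | SD 1.0 | SD 1.5 |
|---|---|---|---|
| 20/20 | 10.4% | 12.3% | 19.3% |
| 20/60 | 9.8% | 14.9% | 18.2% |
| 30/30 | 7.7% | 11.3% | 15.4% |
| 50/50 | 5.9% | 7.4% | 10.1% |
| 100/100 | 6.3% | 5.8% | 8.8% |

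**Arithmetic check.** Expected rejection is roughly 2[1 - Φ(t × SE/SD)]. At 25 per group the critical t on 50 - 6 = 44 df is 2.015.
- Modest: mean SE 0.276, empirical SD 0.314, ratio 0.879; 2.015 × 0.879 = 1.77, giving 7.6% (simulated 8.4%).
- Strong: 0.288/0.420 = 0.686; 2.015 × 0.686 = 1.38, giving 16.7% (simulated 17.8%).

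The shortfall in the standard error accounts for nearly all of the excess.

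**Cause.** In the second design:
- With the true weights known, the default still rejects 7.6% (20/20, SD 0.5) and 10.5% (20/60, SD 1.0), against 10.4% and 14.9% with estimated weights.
- A stacked variance that formally allows for weight estimation makes matters worse: 12.3% to 13.9% (20/20, SD 1.0) and 14.9% to 17.7% (20/60, SD 1.0).
- HC3 with the weights still held fixed gives 3.6-6.3% in every linear cell.

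**Remedies, continuous outcome.**
- Jackknife with refitted weights, first design (300-350 data sets): 9.4% to 4.3% (25, modest), 8.0% to 4.7% (40, modest), 13.0% to 5.0% (40, strong).
- Jackknife, second design (up to 1,000 data sets): 9.0% to 4.2% (20/20, SD 0.5), 10.8% to 3.2% (20/20, SD 1.0), 12.8% to 4.7% (20/60, SD 1.0), 7.5% to 4.4% (50/50, SD 1.0).
- A bootstrap that refits the weights repairs only part: 12.1% to 9.4% (30/30, SD 1.0).

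**Binary endpoint, weighted logistic model.**
- Default, modest imbalance: at about 85% success, 6.7%, 4.9% and 5.3% at 25, 40 and 80 per group; at about 95%, 3.4%, 3.2% and 3.5%. A repeat gave about 5-6%, and about 8-12% under strong imbalance.
- Second design at 90% success: 3.8-5.8%, 6.4-8.4% and 6.9-14.2% for weak, moderate and strong imbalance, with 18-62% of fits not converging at 15-30 per group. At 70% success: 4.8-8.9%, 4.6-13.7% and 8.4-19.1%.
- Jackknife, modest imbalance, about 85% success: 0% at 25 per group and 0.5% at 40 (a repeat: 0-0.3%). At 25 per group, 42 of 237 usable data sets (18%) had a failed refit. At about 95% success, 84 of 99 (85%) failed at 25 per group and 80 of 121 (66%) at 40.

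**The case against.** The strongest reply is that the size of the problem rests on assumptions. No group sizes or imbalance are given, controls come from three earlier studies and may be numerous, and the high figures need a small group and strong imbalance together. That stands, and the figures are conditional. It does not remove the point: the smaller group drives the error, and the plan has no safeguard if that group is small. An analyst could also choose a better variance within the survey package, but nothing in the plan requires it.

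Four stronger readings are tempting and should not be drawn.

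- *The fault is that estimated weights are treated as fixed.* This is at most a smaller part of it. HC3 repairs the error rate with weights held fixed, and the formal correction for weight estimation worsens it.
- *The primary analysis is equally affected.* Its endpoint is binary (sections 2.2 and 5.2). At a high success rate with modest imbalance there is little or no inflation, and separation and non-convergence are the larger difficulty.
- *A false non-inferiority claim becomes more likely by a known amount.* Section 2.3 states: "The study hypothesis to be verified is non-inferiority in term of efficacy between study products and comparator". No margin is given, and the simulations test no difference, so that error rate cannot be computed.
- *Second eyes, or patients present in two control studies, are counted as independent.* The documents do not establish this. Sections 3.1 and 3.2 define eligibility by patient, section 4 refers to one affected eye, and section 5.1 provides a case report form per participant.

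**Conclusion.** The point holds for the continuous visual outcome. With the default standard error and no true effect, a nominal 5% test rejects about 8-9% of the time with 25 in the smaller group and modest imbalance, and up to about 17% with strong imbalance. By 80-150 per group it is about 6-7%, although one strong-imbalance run still gave 9-10% at 80. The main cause is small-sample bias of the sandwich variance; fitting the weights to the same patients adds a smaller part.

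For the binary primary endpoint the rate is about 5-6% at a high success rate and modest imbalance, rising to about 8-12% under strong imbalance. The plan states no success rate, and at an assumed 70% the inflation was larger.

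All of this assumes complete data, a two-sided test, the package default and the simulated covariate structure. Averaging p-values over the 15 imputations is a separate matter and was not tested.

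**What to change.** State in section 4 that, for continuous outcomes, the variance in each imputed data set will be small-sample robust in place of the default linearised one. Two options are suitable: HC3 on the weighted regression, or a delete-one-patient jackknife that refits the CBPS weights and the regression after each deletion (the survey package accepts replicate weights). Name one in advance and base all intervals and tests for these outcomes on it.

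Do not extend the jackknife to the logistic primary endpoint. HC3 is no ready substitute there: at 90% success and 20/20 it rejected 0.0% under moderate and strong imbalance. That endpoint needs its own pre-specified method that copes with separation, checked by simulation at the actual group sizes.

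The cost is SAP wording and, for the jackknife, a loop in the R code. Intervals widen in small groups: by about 10-30% at the median in one simulation, and by up to about 50% on mean standard error in others (for example 0.340/0.277 = 1.23 at 25 per group, modest; 0.358/0.250 = 1.43 at 40 per group, strong). The jackknife is somewhat conservative in the smallest groups, and weights could not be fitted in up to 8% of the 20/20 data sets. With large groups little changes.

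### For binary outcomes the plan pools and tests a conditional log odds ratio, which is neither the average treatment effect it names nor a comparison of success proportions

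*Combined protocol and SAP*

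**What the plan says.** Section 2.3 states: "The study hypothesis to be verified is non-inferiority in term of efficacy between study products and comparator". It adds: "The proportion of success between study products and comparator will be studied". It gives no margin and no effect measure.

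Section 4 says that the Covariate Balancing Propensity Score "will be used to estimate an Average Treatment Effect (ATE"). The outcome models are "linear regressions for continuous outcome variables and logistic regressions for binary variable", fitted with the survey package. These models "will include the treatment group effect, the weight resulting from the matching, and variables present in the propensity score". The propensity variables are "age, gender, visual acuity of the affected eye, surgery type of the affected eye (vitrectomy only vs phaco and vitrectomy").

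Where there are missing values, 15 imputed datasets are analysed and combined by "taking the mean of the estimates of the regression coefficients of the treatment effect", together with the p-values. Section 4 claims of this procedure: "This procedure will provide a doubly-robust estimator, which corrected the last remaining possible imbalance between the covariates and produced an unbiased treatment effect".

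Section 4 also says that results after matching will be shown as means with SDs or as percentages. It plans no between-group difference or confidence interval on the percentage scale. Nothing is said about a group with no failures.

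**The concern.** Three statements in the plan do not fit together for a binary outcome: a question about proportions, a target that is a population-average effect, and a reported quantity that is a covariate-adjusted logistic coefficient. Odds ratios are non-collapsible. Even with perfect weights, adding covariates that predict success moves the coefficient away from the marginal log odds ratio. Double robustness for the average treatment effect belongs to the averaged predictions of the weighted model, not to its treatment coefficient.

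The study's results may inform whether the hospital replaces its current dyes (Section 2.1). A reader who takes the coefficient for the population effect on success cannot recover from it how many percentage points of success are gained or lost. The coefficient also has no finite value when one dye group has no failures. The same holds for any other outcome analysed as yes/no, such as the occurrence of an adverse event. The linear models for continuous outcomes are not affected, because there the coefficient is collapsible.

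**Working it through.** The plan gives no sample size, success rate or margin, so there is no figure of its own to reproduce. All rates, effect sizes and group sizes below are assumptions.

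**1. What a given coefficient means for proportions.** Let success follow a logistic model with treatment effect b and a normal covariate score of standard deviation s. The marginal success probability under dye t (0 = control, 1 = new) is

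p_t = ∫ expit(a + b·t + s·z) φ(z) dz,

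with a solved so that p_0 equals the chosen control success. The difference is p_1 − p_0, and the marginal odds ratio is [p_1/(1−p_1)] / [p_0/(1−p_0)]. With conditional odds ratio 0.50 (b = ln 0.50) and s = 1.0:

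| Control success | New dye success | Difference (points) | Marginal OR |
|---|---|---|---|
| 80% | 68.9% | -11.1 | 0.554 |
| 90% | 82.9% | -7.1 | 0.539 |
| 95% | 90.9% | -4.1 | 0.526 |
| 98% | 96.2% | -1.8 | 0.513 |

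For the 90% row: (0.8291/0.1709) / (0.90/0.10) = 4.851/9 = 0.539. One coefficient therefore corresponds to differences from -1.8 to -11.1 points.

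**2. Dependence on covariate strength and effect size.** At 90% control success and conditional OR 0.50, s = 0.5 gives a marginal OR of 0.510 (-7.9 points), and s = 1.5 gives 0.578 (-6.1 points). With a conditional OR of 0.90, the marginal OR is 0.902 at s = 0.5 and 0.909 at s = 1.0. The odds-ratio gap is then trivial.

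**3. The planned estimator against standardisation of the same fit.** One simulated dataset of 400,000 records was used, with two normal confounders, correct inverse-probability weights and a true conditional OR of 0.50. True success was 80.5% against 87.8%, so the difference is -0.0723 and the marginal OR 0.577. The weighted, covariate-adjusted coefficient gave OR 0.499, which is the conditional value. Averaging that model's predictions for all records under each dye gave a difference of -0.0722, which is the average treatment effect.

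**4. When the coefficient may not exist.** With n eyes per dye and common success p, P(at least one group has no failures) = 1 − (1 − p^n)². For n = 30 and p = 0.90: 0.90^30 = 0.0424, and 1 − 0.9576² = 0.083. The other two columns come from an unweighted simulation with equal groups, no true effects and 300 runs per cell. Each cell shows 90% / 95% success.

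| Eyes in one comparison | A group without failures (formula) | Treatment coefficient non-finite | Separation by any model term |
|---|---|---|---|
| 60 | 8% / 38% | 9% / 41% | 17% / 63% |
| 100 | 1% / 15% | 1% / 14% | 4% / 28% |
| 200 | 0% / 1% | 0% / 1% | 0% / 2% |

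The formula and the simulated rate for the treatment coefficient agree. The last column is larger because it also counts separation on, for example, gender, where the treatment coefficient can stay finite. At 80% success with 30 eyes per dye, the formula gives 0.2%.

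**The case against.** Several points on the other side stand.

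- **No sentence commits the plan to a difference in proportions.** Section 2.3 mentions proportions without an effect measure, Section 4 names an average treatment effect without a scale, and non-inferiority can be framed on an odds ratio. A reader might infer that the plan states an average treatment effect on success proportions. That joins two sections. What remains is that the coefficient is not a marginal effect on any scale, and that it does not deliver a comparison of proportions.
- **The weighted percentages in Section 4 might supply that comparison.** They may, descriptively, so it would be too strong to say that the plan's output can never be read as a difference. But no difference or interval is planned, and the inference rests on the coefficient and its p-value.
- **Near no effect the two odds ratios nearly coincide**, and nothing in the documents shows that the four covariates strongly predict staining. This limits the odds-ratio gap. It does not limit the dependence of the percentage-point difference on control success, which matters because non-inferiority is judged at a margin away from no effect.
- **A reader might infer that the sponsor expects success in nearly all eyes.** The documents do not say so. Section 2.1 speaks of adequate aid, and Section 1 expects Dual View to stain ERM as well as its comparator. Neither gives a rate, and the macular pucker rule in Section 5.2 asks for more than one item.
- **A reader might infer that one separated imputed dataset would dominate the pooled mean.** That can arise only if outcomes themselves are imputed. If outcomes are complete, a group without failures is the same in all 15 datasets.

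**Conclusion.** The point holds for binary outcomes. The pooled and tested quantity is a conditional log odds ratio. The claims of double robustness and lack of bias do not attach to it as an average treatment effect, and it does not give the comparison of success proportions that Section 2.3 raises. The size depends on inputs that the documents do not give. For a conditional OR of 0.50 and covariate SD of 1.0, the implied difference runs from -11.1 to -1.8 points as control success goes from 80% to 98%. The difference between conditional and marginal OR is modest there and negligible near no effect.

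Breakdown is a conditional risk: at 95% success it is substantial with 60 eyes in a comparison (41%), moderate with 100 (14%) and slight with 200 (1%). These rates assume equal groups, no weights and no true effects. Quoting the any-term separation rates as failures of the treatment coefficient would overstate the risk. This should be corrected before analysis.

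**What to change.** Keep the data, weights and covariates.

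1. In each imputed dataset, use the fitted weighted logistic model to predict success for every eye under each dye, and average over all eyes. Report the two standardised success proportions and their difference with a 95% CI, pooled by Rubin's rules, as the primary result.
2. Prespecify one method for a group with no or very few failures, with an interval that stays valid at zero failures. Examples are Firth-type logistic regression with profile-likelihood intervals, or a score-type interval for the difference in proportions. Standardisation alone does not solve this: with no failures in a group, its estimated variance for that group is zero, and an interval built on it is unreliable.
3. Remove the claims that the logistic coefficient is doubly robust and unbiased. If it is still reported, label it a conditional odds ratio.

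The cost is SAP wording and a few lines of R, with no new data. The interval may be wider when failures are sparse.

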### 3.2 Exclusion criteria

Participants eligible for this Study must **not** meet any of the following criteria:

- Children aged <18 years
- Vitrectomy for other indication than mentioned in 3.1
- Patients that have concomitant eye disease that may influence the outcome of the surgery, e.g. terminal glaucoma
- Patients that did not comply to the postoperative examination visit 6-10 weeks after the surgery

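### Section 4 combines the 15 imputed analyses by averaging their p-values, so no valid pooled p-value, standard error or confidence interval is defined

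*Combined protocol and SAP*

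**What the plan says.** Section 4 (Statistics and Data Analysis) states that, if values are missing, "15 multiple imputations will be performed using the" MICE package. In each completed dataset, propensity-score weights are estimated and the survey package is used to "perform linear regressions for continuous outcome variables and logistic regressions for binary variable", with treatment, the weights and the propensity-score covariates in the model.

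The 15 fits are then combined by "taking the mean of the estimates of the regression coefficients of the treatment effect and the its associated p-value for each imputed dataset". The plan gives this rule a name (Mite) and cites a methods paper on propensity scores with partially observed covariates, but it reproduces no formula from that paper. The decision rule follows: "Adjusted P-values less than 0.05 will be considered significant".

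Three other passages matter here:
- Section 4 says that results "will be expressed as the mean and standard deviation (SD) for continuous variables or the percentage for categorical variables". Neither a standard error nor a confidence interval is mentioned.
- Section 2.3 says "The study hypothesis to be verified is non-inferiority in term of efficacy between study products and comparator".
- Section 3.2 excludes "Patients that did not comply to the postoperative examination visit 6-10 weeks after the surgery".

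**The concern.** Multiple imputation produces two kinds of variance: sampling variance within each completed dataset, and variance between datasets, which reflects what is not known about the missing values. A single-dataset p-value uses only the first. Averaging 15 of them does not add the second in any calibrated way, and the average is not uniformly distributed under the null hypothesis. Comparing it with 0.05 is therefore not a level-0.05 test once imputations differ.

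The rule also keeps only a coefficient and a p-value. A weighted regression on one dataset yields a standard error, but the stated pooling step drops it. A non-inferiority conclusion needs an interval, or at least a standard error, to set against a margin. A p-value for no difference cannot provide that. Section 2.1 says the results may inform whether the study dyes replace those now in use, so the precision of the pooled effect matters.

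**Working it through.** **Inputs from the plan.** m = 15 imputations and a significance threshold of 0.05 (Section 4). The threshold's sidedness is not stated; two-sided is assumed. The plan gives no sample size, margin or missing-data rate, so there is no planned figure to reproduce and missingness has to be varied.

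**Formulas.** Let Q_k be the treatment coefficient in imputed dataset k, U the mean within-imputation variance and B the variance of the Q_k. Rubin's rules give:
- estimate = mean of the Q_k
- total variance T = U + (1 + 1/15)B
- degrees of freedom = 14 × [1 + U/((16/15)B)]²

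**One worked case.** Take a mean coefficient of 2.2, U = 1 and a between-imputation SD of 0.5 (B = 0.25), with the 15 estimates spread at normal quantiles.
- Averaged p-value: 0.047, significant.
- Rubin: T = 1 + (16/15) × 0.25 = 1.267; SE = 1.125; df = 14 × (1 + 1/0.267)² ≈ 316; t = 2.2/1.125 = 1.95; p = 0.052, not significant.
- 95% interval by Rubin: 2.2 ± 1.968 × 1.125, or −0.01 to 4.41. With the within-imputation SE alone it would be 2.2 ± 1.96, or 0.24 to 4.16.

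**Type I error, normal theory.** 400,000 null replicates were run per setting, with U = 1. The fraction of missing information (FMI) is taken as (16/15)B/T. For example, FMI 0.20 gives T = 1/0.80 = 1.25 and B = 0.20 × 1.25/(16/15) = 0.234. The estimate from infinitely many imputations is drawn from N(0, U + B), and each imputed estimate adds N(0, B) to it.

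| Assumed FMI | Mean of 15 p-values | Mean coefficient, within-imputation SE only | Rubin's rules |
|---|---|---|---|
| 0 | 5.0% | 5.0% | 5.0% |
| 10% | 5.2% | 6.3% | 5.0% |
| 20% | 5.4% | 8.0% | 5.0% |
| 30% | 5.6% | 10.1% | 5.0% |
| 50% | 6.4% | 16.5% | 5.1% |

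The third column covers the other possible reading of the sentence: the averaged coefficient with a p-value of its own, and no between-imputation variance.

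**A model closer to the plan.** 40,000 null replicates per setting (Monte Carlo error about 0.1 percentage point). Assumptions: 200 eyes, 80% success, four covariates, logistic propensity weights standing in for CBPS, outcomes missing at random given visual acuity, and covariate-adjusted weighted logistic regression with sandwich standard errors.

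| Outcomes missing | Type I error, mean p | Type I error, Rubin | Mean p significant, Rubin not | Rubin SE larger than within-only SE by | Coverage of 95% interval, within-only SE |
|---|---|---|---|---|---|
| 10% | 5.2% | 4.8–4.9% | 0.3% | 5% | 93.7% |
| 20% | 5.5% | 4.8–4.9% | 0.7% | 12% | 91.9% |
| 30% | 5.9% | 4.8–4.9% | 1.1% | 19% | 89.5% |

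Rubin intervals covered 95.1–95.2%. The between-imputation share of total variance averaged 0.10, 0.20 and 0.30. The SE ratios agree closely with 1/√(1 − share) = 1.05, 1.12 and 1.20. The last two columns apply only if an analyst falls back on the within-imputation SE, which the plan does not instruct.

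**The case against.** The sentence contains an editing slip, and it can be read as the averaged coefficient together with that coefficient's own p-value. It also defers to a cited paper, which an analyst would presumably open and which may prescribe standard pooling. On that view the plan is unclear rather than wrong. The point about intention stands, but it does not rescue the rule. The closing reference to each imputed dataset favours averaging the p-values, and the other reading supplies no pooled variance either; with the within-imputation SE alone it does worse. The cited paper cannot be checked from the documents.

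The harm shown for averaged p-values is small: less than one percentage point of type I error up to 30% missing. That stands in full. So does the point that the coverage losses belong to a fallback the plan does not state.

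It can also be said that the plan names no confidence interval even for complete data, so the gap belongs with the missing non-inferiority margin. This is only partly right. A single-dataset regression produces a standard error from which an interval follows directly; the pooling sentence discards it. The absent margin is a separate gap.

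Finally, imputation applies only if values are missing, and the exclusion in Section 3.2 limits missing postoperative acuity. It does not protect the primary endpoint, which Section 5.2 takes from yes/no staining items in surgical reports. The controls come from three earlier studies (Section 2.1), and the plan does not say whether their reports answer those items. The plan also leaves the word adjusted undefined, so taking the tested p-value to be the averaged one is an inference, though the natural one.

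**Conclusion.** The concern holds. As written, the rule yields a p-value that is not valid at 0.05 when imputations differ, and a treatment effect with no pooled standard error or interval. The error in the p-value is modest: 5.2–5.6% in the normal-theory model and 5.2–5.9% in the plan-like model, for 10–30% missing information or missing outcomes respectively, against about 5% with Rubin's rules. The undefined interval is the more serious consequence, because the hypothesis is non-inferiority. There is no effect if the data are complete.

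The missing-data fractions, 200 eyes, 80% success rate, two-sided testing and the stand-in for CBPS are all assumptions, so the decimals are indicative. The direction does not depend on them. This should be corrected before analysis, but the size of the p-value inflation does not make it a critical flaw.

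**What to change.** Replace the averaging of p-values in Section 4 with Rubin's rules, applied to the treatment coefficients and their survey-package standard errors on the planned model scale:
- pooled estimate = mean of the 15 coefficients
- total variance = mean within-imputation variance + (1 + 1/15) × between-imputation variance
- p-value and 95% confidence interval from the t distribution with the matching degrees of freedom

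Report one pooled estimate, interval and p-value for each of the two product comparisons. Put the rule in the text rather than relying on the citation, and say what adjusted means for the p-values.

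The cost is one sentence and a standard pooling call on the 15 models already planned; no new model, effect scale or data are needed. The change does not supply the non-inferiority margin, which has to be set separately.
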